15.0 Risks to Participants*

- 15.1 List the reasonably foreseeable risks, discomforts, hazards, or inconveniences to the participants related the participants' participation in the research.

PROTOCOL TITLE: Non-invasive Vagal Nerve Stimulation in Opioid Use Disorders

- Psychological questionnaires/interview: Being asked questions about the stress in your life or your mood and opioid use may cause you to have unpleasant and/or upsetting feelings or have an increase in opioid craving. If this happens, then you can take a break from the interviews. You can also slow down and take longer to do the tests. Should you so desire, a counseling session and/or referral for counseling will be made available.
- Physiological monitors: (Biopac, Glove, EDA, PPG, SCG, etc.) These monitors require you to have sensors attached to your skin which may represent an inconvenience to you e.g. when adhesives are removed. They may also cause mild skin irritation or itching. The glove cold application may cause temporary numbness, which stops after application. The hot application may cause temporary redness/skin sensitivity. The subject may feel itchiness due to sensor hookups on hands (due to sticky electrodes and gels) and temporary numbness of the arm is possible, since the subject will remain in the same position for half an hour. The EDA requires you to wear a bracelet-type device during (and possibly after) the visit, which may represent an inconvenience to you.
- Intravenous (IV) catheter and blood draw. The IV can result in infection, bruising of the skin, or a blood clot in the vein. These complications are not common when the catheter is inserted by a professional under clean conditions. Dizziness and fainting are rare risks of blood draws. There are no long-term side effects. The subject may have some discomfort from the blood drawing. The risk from blood drawing is minimal, but may include bruising and infection. The use of sterile precautions will decrease the risk of infection. However, the subject may develop a bruise at the site of the puncture, but this is expected to go away in two to three days.
- PET scan: This research study involves exposure to radiation from a Positron Emission tomography (PET) scan. This PET scan procedure is routinely used for medical purposes; however, radioactive water is investigational and not approved by the FDA. This radiation dose is not necessary for a subject's medical care and will occur only as a result of the subject's participation in this study. If a subject has had any significant exposure to radiation over

PROTOCOL TITLE: Non-invasive Vagal Nerve Stimulation in Opioid Use Disorders

the past year or plans to participate in other research studies involving radioactivity over the next year, he/she should consult with the study team and [name] first. Some people experience anxiety from the PET scan procedure. Viewing videos on smart glasses may cause wooziness or motion sickness. A nurse or technologist will be with the subject during the PET scan procedure. If a subject becomes claustrophobic, anxious or agitated in the PET scanner, the scan will be stopped. If a subject is not able to complete the first PET scan, he/she may not be able to continue in the study. This study will expose subjects to a small amount of radiation. The radiation dose that subjects will receive is equal to or less than the annual radiation exposure limit allowed for persons who are occupationally exposed to radiation (x-ray technicians, radiologist). The principal risk associated with a radiation does is the possibility of developing a radiation-induced cancer later in life. The risk for radiation-induced cancer from this study is minimal. Although the risk from radiation is cumulative it is not expected to adversely affect a subject's condition or treatment. The risk from radiation exposure of this magnitude is considered to be comparable to other everyday risks.

- MRI scan: There is the risk that if subjects have indwelling metallic foreign bodies in the head that MRI scanning may cause local tissue damage. All subjects will be screened for indwelling foreign bodies and individuals with indwelling bodies will be excluded. Some individuals may feel anxiety while in the scanner. If needed, the study will be stopped. There are no other risks of MRI scanning.

Subjects will be getting a scans (PET/MRI) for research purposes only. The research does not require the scans to be read for healthcare purposes. However, if the researchers are concerned about something they see on the scans they will tell the subject, and ask if he/she wants the scans to be reviewed for healthcare purposes (possibly by other clinicians), and he/she may then be referred for medical treatment.

- Opioid Use Related Videos. The viewing of opioid use related videos may cause some anxiety or feelings of craving for opioids. Subjects are able to stop this test at

PROTOCOL TITLE: Non-invasive Vagal Nerve Stimulation in Opioid Use Disorders

any time if they experience anxiety, excessive cravings, or other problems or are uncomfortable with the procedure.

- **VNS Testing.** Sometimes, a subject may experience hoarseness, shortness of breath, throat pain, cough, abdominal pain, headache, and/or change in voice during treatment. A tingling/pricking/twitching feeling where the device is applied is normal, but should not cause major discomfort. These effects usually stop right away once the treatment is completed. Mild skin irritation or dizziness are other possible side effects. The VNS device should not be used on patients who have any of the following conditions: an active implantable medical device, such as a pacemaker, defibrillator, cochlear implant, and other implanted electronic device; a history of significant carotid atherosclerosis; or a cervical vagotomy.
- **Reproductive Risks.** Since this research may have bad effects on a fetus and should not be done during pregnancy, it is necessary that a pregnancy test be done first, even if, to the best of the subject's knowledge, they are not pregnant now. Women of childbearing potential will take a urine pregnancy test when they arrive for their visits. If the test is positive they will not be able to participate in the study. This study may be hazardous to a breast-feeding child. Breast feeding mothers may not participate in this study.

Women who may be pregnant should not be in this study because of possible effects of radiation exposure on their unborn child. Both men who may later father children and women of childbearing potential should be aware that exposure to radiation poses a very slight risk of genetic mutation in the next generation.

- **Fasting.** In order to undergo study testing, subjects need to be fasting before their study visit for the scan day until the scans are completed. Some people may show discomfort from this prolonged fasting, although true hypoglycemia is rare. A sweetened beverage will be administered if patients complain of lightheadedness or other fasting-related symptoms.

15.2 The long-term effects of the chronic use of VNS have not been evaluated.

15.3 The PET scans and VNS testing may have risks to an embryo or fetus should the subject be or become pregnant.

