10.0 Inclusion and Exclusion Criteria*

10.1 Inclusion and exclusion criteria are listed below. Potential participants will be screened for eligibility by a staff member. We will try to pre-screen subjects via phone using a verbal consent and a waiver of documentation when possible. Otherwise, potential subjects will come in for a screening visit. At the first visit, study staff will confirm eligibility using a checklist.

10.2 The Inclusion and Exclusion Criteria for Study #1: Subjects aged 18 and over who: 1) meet criteria for OUDs based on DSM-5 criteria. The Inclusion and Exclusion Criteria for Study #2: Subjects aged 18 and over who: 1) meet criteria for OUDs based on DSM-5 criteria; 2) have IV access.

Exclusion Criteria: 1) positive pregnancy test; 2) meningitis; 3) moderate traumatic brain injury; 4) neurological disorder or organic mental disorder; 5) history of loss of consciousness greater than one minute; 6) current pregnancy or breastfeeding for women; 7) current or lifetime history of schizophrenia, based on the SCID; 8) a history of serious medical or neurological illness, such as cardiovascular, gastrointestinal, hepatic, renal, neurologic or other systemic illness; 9) evidence of a major medical or neurological illness that is based on the clinical judgment of the study psychiatrist; 10) carotid atherosclerosis; 11) cervical vagotomy.

PROTOCOL TITLE: Non-invasive Vagal Nerve Stimulation in Opioid Use Disorders

Several of the above exclusions will be based on the clinical judgment of the study physician. If reviewed and deemed acceptable by the study physician some exclusions may not preclude participation.

10.3 The following populations will also be excluded from the research:

- Adults unable to consent
- Individuals who are not yet adults (infants, children, teenagers)
- Pregnant women
- Prisoners

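### The exclusion list in 10.2 omits active implanted devices, one of the three conditions in which 15.1 says the VNS device should not be used, and the physician waiver protects neither of the other two

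*Combined protocol and SAP*

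**What the plan says.** Section 15.1, under VNS Testing, sets out when the device is contraindicated: "The VNS device should not be used on patients who have any of the following conditions: an active implantable medical device". It gives pacemakers, defibrillators, cochlear implants and other implanted electronics as examples. It then adds a history of significant carotid atherosclerosis, and cervical vagotomy.

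Section 10.2 has 11 numbered exclusions, the last two being "10) carotid atherosclerosis; 11) cervical vagotomy". Two broader items cover illness: "8) a history of serious medical or neurological illness, such as cardiovascular, gastrointestinal, hepatic, renal, neurologic or other systemic illness" and "9) evidence of a major medical or neurological illness that is based on the clinical judgment of the study psychiatrist". Section 10.3 adds adults unable to consent, minors, pregnant women and prisoners.

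Section 10.2 then allows exceptions: "If reviewed and deemed acceptable by the study physician some exclusions may not preclude participation". It does not say which exclusions this covers.

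On how eligibility is applied, 10.1 says: "At the first visit, study staff will confirm eligibility using a checklist". The checklist itself is not part of the document.

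**The concern.** Eligibility is decided from the criteria in section 10 and the checklist that applies them. Section 15.1 is a description of risks, partly addressed to the participant. If a contraindication to the study device appears only there, staff working from the criteria can enrol and stimulate someone who should not be stimulated.

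The other two device contraindications were carried into 10.2, so this looks like a drafting omission and not a deliberate choice. The sponsor already accepts that an active implant rules out stimulation, so no clinical judgement is in dispute.

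The open-ended waiver is a second, lesser point. It does not name vagotomy or carotid disease as waivable, but it does not rule that out.

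What is at stake is participant safety. No endpoint, analysis or sample size is affected. Section 6.5 has the user raise stimulation to the highest tolerable level, and 9.1 and 13.3 allow for some participants taking a device home. Section 16.1 says the study is not designed to benefit participants directly, so nothing offsets the omission.

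**Working it through.** There is no planned figure to reproduce. The check compares the texts and counts.

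**Step 1. Conditions for which 15.1 keeps a person out, against 10.2.**

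| Condition in 15.1 | In 10.2? |
|---|---|
| Active implanted device | No |
| Significant carotid atherosclerosis | Yes, item 10 (worded more broadly, without a severity limit) |
| Cervical vagotomy | Yes, item 11 |
| Indwelling metal (MRI) | No |
| Pregnancy | Yes, items 1 and 6 |
| Breastfeeding | Yes, item 6 |

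For pregnancy, 15.1 says "If the test is positive they will not be able to participate in the study", and 10.2 matches it with "6) current pregnancy or breastfeeding for women".

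- Device contraindications: 3 in 15.1, 2 in 10.2, so 3 − 2 = 1 is missing.
- All conditions: 6 in 15.1, 4 in 10.2, so 6 − 4 = 2 are missing.
- Numbered items in 10.2 that name an implant: 0 of 11. Section 10.3 adds none.

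**Step 2. What else would catch an implant carrier?**

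- *Illness exclusions (items 8 and 9).* These probably reach most pacemaker and defibrillator carriers through the underlying heart disease. They name illnesses and not devices, and the waiver does not set them apart.
- *Metal screen for MRI (6.6 and 15.1).* Under 6.4 every participant in both studies has an MRI. Section 15.1 screens everyone for indwelling foreign bodies and excludes those who have them. This would probably catch a cochlear implant. Both sections, however, describe the hazard as metal in the head, and neither says whether the screen comes before stimulation.
- *Timing.* For Study 2, the payment list in 13.3 places the PET day at Visit 2 and the MRI day at Visit 3. For Study 1 it pays the MRI and the visit together. A payment list is not a procedure schedule and does not date the screen, so timing is unstated, not shown to be wrong.

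**Step 3. What remains.** Of the 4 implant types in 15.1, these provisions probably reach 3 (pacemaker, defibrillator, cochlear implant). That leaves 4 − 3 = 1, the residual class of other implanted electronics. A carrier is caught only if the metal screen is read as covering the whole body and is done before stimulation. An implanted stimulator for pain would be an example. This is an illustration and does not come from the documents, but pain is measured in this population (6.3) and is not an exclusion.

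**Step 4. The waiver.** Of the 2 device contraindications that 10.2 does list, 0 are marked as non-waivable.

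**The case against.** The strongest reply is that the prohibition is already in the protocol. Section 15.1 is part of the same document, so stimulating an implant carrier would depart from the plan as written. On this view only a cross-listing is missing. That is correct as far as it goes: this is an omission and not a contradiction. But 10.2 is where the exclusions are listed, and a contraindication to the study intervention belongs there.

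Second, the sentence in 15.1 that screens for and excludes indwelling bodies is not itself limited to the head, and an exclusion would normally be applied at screening. Both are fair readings, and nothing in the documents places the screen after stimulation. Neither is stated, however, and closing the gap depends on both.

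Third, the waiver follows a sentence about exclusions that rest on clinical judgement. It can be read as covering only items such as 8 and 9, and 15.1 carries no waiver of its own. That reading is plausible, and it makes the waiver the weaker half of the point. The text still does not say which exclusions may be set aside.

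Finally, the checklist is not shown and may already ask about implants. This stands. Together with the other safeguards, it is why the residual risk is small.

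**Conclusion.** The concern holds and should be fixed. One of the three device contraindications in 15.1 is missing from 10.2, and neither of the two that are listed is protected from waiver. The wording comparison is certain. The practical gap is less so, because it depends on how the metal screen is read, when it is done, and what the checklist contains.

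The group left exposed is narrow: people with an active implant outside the head that was not placed for an excluded illness. The documents give no implant frequency, so no expected number can be calculated for the 60 enrollees requested in 12.2. It is likely very small.

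**What to change.** 1. Add active implantable medical devices to 10.2 and to the eligibility checklist, naming pacemakers, defibrillators, cochlear implants and any other implanted electronics. Require confirmation before any stimulation.
2. List indwelling metal in 10.2 as well, since 15.1 already excludes it.
3. State that the study physician may not waive the three device contraindications: active implant, significant carotid atherosclerosis and cervical vagotomy. Carotid disease that is not significant may stay waivable, which matches the narrower wording of 15.1.

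The cost is a short text amendment to 10.2 and the checklist, and one screening question. Procedures and sample size do not change.

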16.0 Potential Benefits to Participants*

16.1 This study is not designed to directly benefit participants.

17.0 Data Management* and Confidentiality

17.1 We will use analysis of variance models with change in blood flow as dependent variable and absolute blood flow during control task as well as study group as explanatory variables. This analysis will assess differences in brain function according to diagnosis correcting for potential differences in baseline (control task) values. The ANOVA model will be blocked by the matching factor of past alcohol exposure. Analyses will be adjusted for whole brain blood flow. Additional control factors, including patients' age, age of onset of traumatization, years of education, IQ, OUD symptom level and duration of disease, use of oral contraceptive birth control, and smoking, will be entered in the model if they are significantly different between the study groups at an alpha level of 0.25, and/or if they are found to be confounders in the analysis, i.e., if they cause a change of >10% in the parameter estimate for study group when entered in the model. Adjusted means of blood flow will be computed for each combination of group and task to better describe the results. Point estimates and confidence intervals for the difference between groups will be assessed before and after including the covariates mentioned above in the model. Additional analyses will compare OUD patients with and without a history of co-morbid depression.

In all these analyses linear model assumptions, adequacy of fit, and presence of outliers will be checked by inspecting residual plots and influence statistics. Collinearity for variables included in the model will also be checked. Appropriate remedies will be applied, if necessary, to improve model fit and minimize collinearity.

Additional exploratory analyses will use subtraction analysis techniques to look for additional areas of activation for the purpose of generating hypotheses for future studies. Images of absolute blood flow will be subjected to a subtraction type analysis. Images will be realigned to the first image in the series and warped into a common anatomical space using methods described in the preliminary results. Images will be then analyzed using the general linear model of Friston for statistical analysis. The mean of blood flow scans within condition will be calculated and comparisons performed between conditions to assess blood flow with the condition. Areas of increased and decreased blood flow within patient group will be examined, as well as the interaction between

PROTOCOL TITLE: Non-invasive Vagal Nerve Stimulation in Opioid Use Disorders

condition and diagnostic group. Images of t statistic will be created and surveyed for hypothesized regions (i.e. medial prefrontal cortex) where uncorrected z score values are greater than 2.86 (corresponding to a corrected p value of > 0.005).

Calculation of Sample Size

For calculation of sample size needed for PET measurement of anterior cingulate activation, we used values for blood flow in the amygdala (scaled to whole brain blood flow) based on previous pilot data. Fear-related tasks resulted in a $6.9 + 4.8\%$ increase in amygdala blood flow versus $1.2 + 1.4\%$ in controls (effect size 1.39). With two tails, an alpha value set at 0.05 and a power of 0.80, 10 subjects are needed in each group (VNS v sham) to show a significant difference between patients and controls (i.e. group by condition interaction). The number of subjects in each group will therefore be adequate to answer the questions proposed in this study.

- 17.2 All study staff will take required training prior to working with participants and/or PHI. All data will be kept in either locked offices in secure buildings or online via Redcap or on a password restricted research server. A certificate of confidentiality will be in place. Confidentiality will be assured by the use of subject codes when possible rather than personal identifiers. After the study is completed, the study database will be secured, and information will only be entered using subject identifier codes rather than personal identifiers. Published results will be presented as group data, without identifiers.
- 17.3 A (bi) weekly meeting with the staff, Study Coordinator and the PI is held to discuss any issues that may arise. A review of data is done for accuracy and protocol compliance. Data collection forms are verified for accuracy before storing in database. Describe any procedures that will be used for quality control of collected data.
- 17.4 Describe how data or specimens will be handled study-wide:
 - Study ID, date of visit, and type of sample will be included for each specimen
 - Specimens will be stored in a -80 freezer at EP12 or RSPH
 - Specimens will be stored until they are fully utilized for testing
 - The [name] Lab and the study team will have access to the data and/or specimens
 - The [name] Lab uses a spreadsheet system to inventory what has been brought to their lab for testing. A study team member will deliver the samples and the lab will sign off on

the delivery. The data will be sent from [name] to the PI and/or study staff for saving to the research server.

- Specimens will be transported via dry ice using coolers from Wesley Woods and/or EP12 to the [name] Lab in RSPH.

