6.0 Procedures Involved*

- 6.1 Study Design: Study #1: This is a randomized dose finding study of nVNS versus sham stimulation in patients with a history of Opioid Use Disorders (OUDs). This study will optimize dosing (N=20) by testing different stimulation duration parameters. We will measure how these different parameters affect drug craving using analogue scales (248) as well as physiological signals with wearable sensing devices.

6.2

Study #2 is also in patients with OUDs whose aim is to measure brain and biological correlates of nVNS versus sham in conjunction with exposure to drug use cues (N=20). Active and sham devices are assigned serial numbers by ElectroCore Inc. and delivered to the Data Manager who keeps the blind and assigns to subjects as they are recruited using a random number generator. Subjects then undergo nVNS or sham over one day in conjunction with control neutral versus drug use videos to stimulate craving in conjunction with nVNS or sham with brain imaging, measurement of biomarkers and collection of wearable sensing device data. We proceed to the UH3 phase which is a larger study in OUD patients if the goals of the UG3 phase are met per NIDA. Only the UG3 phase is covered here. We hypothesize a decrease in sympathetic function and interleukin 6 (IL-6, an inflammatory marker) enhanced anterior cingulate function with VNS.

- 6.3 All subjects undergo assessment with behavioral measures, including the SCID (245, 246), a craving measure called the Clinical Opiate Withdrawal Scale (COWS) (248), the SHAPS-C, NRS pain scale, Addiction Severity Index, The Snaith Hamilton Pleasure Scale-Clinician (251), the Subjective Units of Distress Scale (263) The Visual Analogue Scale (VAS) consists of 10-point lines anchored with "not at all" on one end and

PROTOCOL TITLE: Non-invasive Vagal Nerve Stimulation in Opioid Use Disorders

"extremely" on the other where participants report the extent to which they felt any craving for opiates, severity of withdrawal symptoms, and the extent to which the study intervention has helped to ease the cravings.

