Medical History, is taken with a structured questionnaire which assess socio-demographic factors, medical history, handedness, history of substance use, medications including antidepressants, mood stabilizer and antipsychotics, usage will be quantitated for number of years of usage for utilization in additional analyses. Urine drug testing may be done at study visits. The Early Trauma Inventory (ETI) is 56-item instrument for measurement of childhood traumatic experiences which has been shown to be reliable and valid. All subjects will be assessed with both the ETI-SF-SR for events before the age of 18 and the Adult Trauma Inventory (ATI) for after age of 18. Reinforcement Learning Task (Positive and Negative Valence Domain): Measures reward attainment using an instrumental conditioning task (90 trials). Trials for this task involve a 3s cue presentation during which subjects choose between two abstract stimuli, followed by an exponentially jittered delay, and then a 3s feedback presentation with positive (monetary win), negative (monetary loss) or neutral outcomes. Reward Motivation Task (Positive Valence Domain): Effort-Expenditure for Rewards Task (EEfRT) is a multi-trial game in which participants are given an opportunity on each trial to choose between two different task difficulty levels in order to obtain monetary rewards.

Study #1: Description of Research Procedures, Monitoring for Safety and Minimization of Risks: Patients with OUDs will undergo stimulation at the different parameters outlined. Subjects will first be outfitted with wearable sensing devices (patches attached to the chest and arms) for measurement of physiological signals including the electrical rhythm of the heart (electroencephalogram) as shown in the figures. These figures outline how parameters of interest like PEP and PPG amplitude are measured. Craving is measured with visual analogue scales. Patients will undergo VNS or sham stimulation while viewing neutral and opioid use related videos.

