6.4 Magnetic Resonance Imaging (MRI) of the Brain: Subjects in both Study #1 and Study #2 will undergo MRI brain imaging at CSI for identification of the vagus nerve in the neck. Sequences to be obtained include volumetric interpolated breath-hold examination (VIBE), TR=4.93, TE=2.46, flip angle=9, Field of View 210 mm, 112 slices, voxel .78 x .78 x .8, averages 3, time of acquisition 4:38. 3D constructive interference in steady state (CISS), TR=5.46, TE=2.43, flip angle=42, Field of View 152 mm, 112 slices, voxel .6 x .6 x .6, averages 1, time of acquisition 5:17.

6.5

For Study #2 we look at physiology with nVNS or sham in OUD patients. Brain function will be measured with high resolution positron emission tomography (HR-PET) (264-270), autonomic function with wearable sensing devices, and biomarkers will be measured in blood, with an assessment of a broad range of stress responsive sympathetic, hormonal and immune markers. A

complete outline of study procedures for Study #2 is presented in Figure 4.

After initial set up and rest period subjects will rest for 30 min. Next, subjects will undergo a series of viewing exercises while lying in the High Resolution Positron Emission Tomography (HR PET) scanner with physiologic monitors attached. After an initial baseline period of resting (condition 1), the subjects will then view two neutral 120 second videos (condition 2), followed by a playback of two opioid use related videos (condition 3). The subject will be instructed to image each event as vividly as possible. VNS or sham will be randomized and given during exposure to the videos. For two of the scans, we are looking at effects of nVNS on the brain with no intervention. The subjects will undergo nVNS vs. Sham VNS stimulation as per published methods (see above).

The VAS and SUDS and other behavioral measures are assessed in the beginning and after each task to assess the efficacy of the

[figure not shown]

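### On the natural reading, the PET model in 17.1 adjusts for flow measured under randomised stimulation, so its group coefficient is not the interaction on which the study was sized

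*Combined protocol and SAP*

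**What the plan says.** **The model.** Section 17.1 takes "change in blood flow as dependent variable and absolute blood flow during control task as well as study group as explanatory variables". It gives the purpose of the covariate as "correcting for potential differences in baseline (control task) values". It does not say which scans are the control task.

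**The sizing.** The sample size paragraph in the same section states that "10 subjects are needed in each group (VNS v sham") "to show a significant difference between patients and controls (i.e. group by condition interaction"), using an effect size of 1.39, two-sided alpha 0.05 and power 0.80.

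**Text suggesting that the control scans are stimulated.** Section 6.2, on Study #2, refers to "control neutral versus drug use videos to stimulate craving in conjunction with nVNS or sham". Section 6.5 lists rest, two neutral videos and two opioid videos, and then says "VNS or sham will be randomized and given during exposure to the videos", with no exemption for the neutral ones. For Study #1, section 6.3 is explicit: "Patients will undergo VNS or sham stimulation while viewing neutral and opioid use related videos". Study #1 has no PET, so that sentence supports the reading only by analogy.

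**Text pointing the other way.** Section 6.5 uses the word baseline for rest: "After an initial baseline period of resting (condition 1"). Sections 1.0 and 2.1 link stimulation to drug cues. Section 6.5 describes only a first and a second delivery and ties neither to a video type. It also mentions two scans of nVNS without a task, so that count may be incomplete. The full Study #2 schedule is in Figure 4, which is not readable in the text reviewed.

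**The expected effect.** Section 2.3 hypothesises enhanced anterior cingulate function with VNS in general, and section 4.1 makes enhanced anterior cingulate function part of the primary endpoint. Neither limits it to drug cues.

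**The concern.** Adjusting change for a true baseline is sound and usually gains power. The adjustment works because a baseline cannot be affected by the randomised treatment. A scan taken while nVNS or sham is running lacks that protection: if nVNS moves neutral-video flow, the covariate carries part of the treatment effect, and the model no longer estimates the contrast that was sized.

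What is at stake is the interpretation of the main PET result. If nVNS raises anterior cingulate flow whatever is on the screen, the model can report a cue-specific effect that is absent, or inflate one that is real. The rest of 17.1 does not settle the matter:

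- The adjusted means by group and task are descriptive.
- The subtraction analysis does examine a condition-by-group interaction, but it is labelled exploratory.
- Estimates are promised with and without covariates, but 17.1 does not say whether control-task flow is one of those covariates or which estimate is the main one.

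**Working it through.** **1. The plan's own figure.** With effect size 1.39, two-sided 0.05 and power 0.80, the normal approximation gives 2 × (1.960 + 0.842)² / 1.39² = 8.1, so 9 per arm. The noncentral t gives 10 per arm, with power 0.836 at that size. The stated 10 per group reproduces. The value 1.39 is taken as stated.

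**2. What the group coefficient estimates.** Let D and N be drug-cue and neutral flow, Y = D − N, δ_D and δ_N the nVNS-minus-sham effects on each, and b the within-arm slope of D on N. The slope of Y on N is then b − 1, and the arm coefficient after adjusting for N is

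(δ_D − δ_N) − (b − 1)δ_N = δ_D − bδ_N = interaction + (1 − b)δ_N.

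It equals the interaction only if δ_N = 0 or b = 1.

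**3. Assumptions.** From the documents: 10 per arm, two-sided 0.05, interaction 1.39. Interpretations: study group means VNS v sham (17.1 also speaks of diagnosis, but all participants have OUD), and change means drug-cue minus neutral. Not in the documents, so assumed: correlation ρ of 0.5, 0.7 or 0.9 between the two flows; equal variances, so that b = ρ; δ_N from −1 to +1 SD of a single scan; no dropout. Whole-brain-flow adjustment and blocking on alcohol exposure are not modelled.

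**4. Bias in units of the SD of change.** The SD of change is √(2(1 − ρ)) single-scan SDs, so the bias per 1 SD of δ_N is (1 − ρ)/√(2(1 − ρ)) = √((1 − ρ)/2). For ρ = 0.5/0.7/0.9 this is 0.50/0.39/0.22.

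**5. Simulation, 60,000 trials per cell.** Rejection rates in per cent for ρ = 0.5/0.7/0.9:

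| True interaction (SD of change) | δ_N (SD of one scan) | Planned model | Unadjusted D − N |
|---|---|---|---|
| 0 | +0.5 | 8.8 / 7.1 / 5.5 | about 5 |
| 0 | +1 | 18.6 / 12.4 / 7.1 | about 5 |
| 1.39 | 0 | 90.8 / 87.1 / 82.9 | about 84 |
| 1.39 | +1 | 96.9 / 92.7 / 84.9 | about 84 |
| 1.39 | −0.5 | 74.5 / 72.9 / 73.9 | about 84 |
| 1.39 | −1 | 46.9 / 51.3 / 59.0 | about 84 |

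With a true interaction of 1.39 and δ_N = +1, the planned coefficient averages 1.89/1.78/1.61, which is 1.39 plus the bias in step 4.

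**The case against.** **The premise is not settled.** Figure 4 may state which scans carry stimulation. In 6.5, the videos can be read as the opioid videos just described. Section 6.6 gives eight blood-flow scans: at one scan per video, two neutral, two opioid and two nVNS-only scans leave 8 − 6 = 2, plausibly rest and unstimulated. All of this stands, and it is why the point is conditional. Against it, rest is not naturally a task, 6.2 attaches the word control to the neutral videos, and 6.5 exempts none of the videos. A reader might infer that the neutral scans are certainly stimulated and the model therefore invalid; the documents do not support that.

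**The loss of power needs an effect against the hypothesis.** A reader might infer from the last rows of the table that power falls to 47–59%. That requires nVNS to lower neutral cingulate flow by 1 SD, whereas 2.3 expects enhancement. It also implies a drug-cue effect of 1.39 × √(2(1 − ρ)) − 1 = +0.39/+0.08/−0.38 single-scan SDs. In the hypothesised direction the planned model loses no power. This objection stands, and loss of power is secondary.

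**The inflation may be small.** At 0.5 SD, rejection is only 9/7/6%. A 1 SD neutral effect is large: 1.0/1.3/2.2 SDs of change. At ρ = 0.9 the excess is slight throughout. This stands too, since the documents give neither ρ nor δ_N.

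**An interaction test can miss what the trial wants to know.** If nVNS raises flow equally in both conditions, the hypothesis in 2.3 is true, yet the unadjusted contrast rejects in only 5% of trials. This is a real limitation, and the fix must allow for it. It does not rescue the planned model, whose coefficient is neither the interaction nor the general effect.

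**Conclusion.** The point holds as a conditional. On the natural reading of 6.2 and 6.5, the covariate in 17.1 is measured after randomisation and under stimulation, and the group coefficient is the interaction plus (1 − b)δ_N rather than the interaction on which 10 per arm were sized. If nVNS raises neutral flow, as 2.3 makes plausible, the coefficient is biased upward by 0.50/0.39/0.22 SDs of change per single-scan SD of neutral effect. False rejection then lies between about 6% and 19% over the assumed positive neutral effects, and a true 1.39 can appear as 1.61 to 1.89.

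If the control-task scans are unstimulated, or nVNS does not affect them, the planned model is valid. The point does not change the sample size. Confidence is medium: the algebra is certain, but the premise depends on a schedule that could not be read and the size on assumed values. It should be fixed, because the remedy is cheap and is needed before anyone sees the PET data.

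**What to change.** In 17.1:

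1. Identify the control-task scans and state which scans carry stimulation, in agreement with 6.5 and Figure 4.
2. Allow as a flow covariate only flow measured before or without stimulation.
3. If the neutral scans are stimulated, make the test of the sized interaction the between-arm comparison of drug-minus-neutral flow, or an equivalent group-by-condition model, without neutral flow as covariate. Report the nVNS effect within each condition alongside it, because the interaction test does not detect a general nVNS effect on the endpoint in 4.1.
4. If the neutral scans are unstimulated, keep the planned adjustment.

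**Cost.** Wording and a little more analysis; no new participants, scans or procedures. If the neutral scans are stimulated but unaffected, power is about 84% instead of 91/87/83% for ρ = 0.5/0.7/0.9, a loss of about 7 points, 3 points and none. That is still above the planned 80%. If the neutral scans are unstimulated, nothing is lost.
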